6.2 Description of Evaluations

6.2.1 Screening Evaluation

Consenting Procedure

We are requesting a waiver of informed consent per 45 CFR §46.116 f 3 (i-v). Please see section 4.3 for details.

6.2.2 Enrollment, Baseline, and/or Randomization

Enrollment

This is a pragmatic trial. Using Bluestone's EHR, research staff will identify potentially eligible ALCs which have at least 10 residents with a dementia diagnosis (ICD-10) who are full code or missing code status at baseline. Bluestone will enroll ALCs. Bluestone will have discretion to exclude potentially eligible ALCs prior to randomization based on information on competing interventions or other relationship characteristics with ALC.

Randomization

Stratifying by state and balancing on baseline use of advance directives, number of Bluestone residents in the ALC, and resident clinical characteristics, a Brown statistician will randomize 160 ALCs to the intervention or control study arms (80 ALCs per arm).

6.2.3 Follow-up Visits

There will be no direct follow-up for residents / proxies in ALCS randomized to usual care or information only study arms.

6.2.4 Completion/Final Evaluation

There are no completion, final evaluations. Outcomes will be evaluated using EHR data

7 SAFETY ASSESSMENTS

7.1 Adverse Events and Serious Adverse Events

Adverse Event (AE) Definition: AE is any untoward or unfavorable medical occurrence in a human study participant, including any abnormal sign (e.g. abnormal physical exam or laboratory finding), symptom, or disease, temporally associated with the participants' involvement in the research, whether or not considered related to participation in the research.

AEs for this study include:

The potential AEs that could occur during this trial are negative emotional reactions when patients or family members watch ACP video or talk to a clinician about resident care preferences. Negative emotional reactions may include feelings of anxiety, worry or sadness. Negative emotional reactions resulting from watching the ACP video or talking to a clinician about resident care preferences would be classified as mild because the distress is easily tolerated and/or remediated, requires no medical evaluation, and has signs and symptoms that are transient. An immediate, negative reaction to watching the video or having a conversation with a clinician would fit the study relatedness category "Definitely Related." AEs resulting from negative emotional reactions to the intervention are expected but likely rare. Our prior testing of a similar ACP video in a nursing home population with dementia demonstrated high user acceptability and few negative emotional responses. We believe the intervention does not incur any greater distress than usual ACP practices.

Serious Adverse Events (SAE) Definition: SAEs consist of any adverse event that results in death; is life threatening or places the participant at immediate risk of death from the event as it occurred; requires or prolongs hospitalization; causes persistent or significant disability or incapacity; results in congenital anomalies or birth defects; is another condition which investigators judge to represent significant hazards

SAEs for this pilot study include:

No serious adverse events (SAEs) are expected, as this intervention does not contain any components with the potential to be life threatening, require or prolong hospitalization, cause persistent or significant disability or incapacity, or result in congenital anomalies or birth defects.

7.1.1 Reporting Procedures

Process for identifying AEs and SAEs:

As part of Bluestone clinician training, instructions will be given as to what constitutes an AE / UP and how to report potential AEs / UPs to study staff. Bluestone clinicians will be instructed to offer to end a conversation, or have a conversation at another time, if a resident or proxy seems to be experiencing emotional distress as a result of their discussion. The Bluestone staff should report any potential AEs / UPs to the study project manager within one day of the event by calling or emailing the study project manager

(contact information provided during training). All potential AEs / UPs will be investigated and a Event Reporting Form will be completed and submitted to the PI via email within 24 hours of the project manager becoming aware of the event. Similarly, contact information for the study project manager will be provided at the end of the outreach letter. All potential AEs / UPs reported by study participants will be investigated and a Event Reporting Form will be completed and submitted to the PI via email within 24 hours of the project manager becoming aware of the event.

7.1.2 Follow-up for Adverse Events

Upon receipt of the Event Reporting Form, the PI and [name] complete the Event Verification Form. [name] is a co-investigator on the project and a board-certified geriatrician with ACP experience. Specifically, the PI and [name] will review the details of the event, confirm that the event meets criteria for a true AE / UP, and classify the severity, expectedness, and relatedness of the event.

During verification, if it is determined that the event does not meet the criteria for a true AE / UP, the Event Reporting Form and the Event Verification Form will be retained by the study team, and no further action will be taken. During verification, if it is determined that the event meets the criteria for a true AE / UP, we will follow the reporting schedule detailed below.

During verification, if it is determined that the event is a true AE, the Event Reporting Form and the Event Verification Form will be retained for quarterly reporting of AEs to the Safety Officer (SO), the NIA Program Officer, and the IRB. A summary of AEs will be included in the annual DSMB report.

During verification, if it is determined that the event is a true UP, the PI will notify the safety officer, the SO, the NIA Program Officer, the Office for Human Research Protections, and the IRB within 24 hours of the research team becoming aware of the event (within 48 hours of the event occurring). The Event Verification Form will also be used to capture the follow-up status of a resident who has experienced a UP. The Event Reporting Form and the Event Verification Form will be retained and a summary of UPs will be included in the annual DSMB report.

7.2 Safety Monitoring

8 INTERVENTION DISCONTINUATION

We do not include stopping rules for two reasons. First, this is a minimal risk study for which AEs will be rare. Second, a stopping rule would not be very feasible since the implementation period is less than one year— which means that interim data analyses will be difficult, if not impossible, to perform until the intervention is nearly complete.

9 STATISTICAL CONSIDERATIONS

9.1 General Design Issues

The primary objective of this embedded, pragmatic, cluster-randomized trial (ePCT) is to test the effects of a COVID-specific, advance care planning (ACP) intervention on documentation of do-not-resuscitate (DNR) orders in a target cohort of assisted living community (ALC) residents with dementia from 160 ALCs in FL, MN and WI.

ALC residents with dementia who are full code or missing code status at baseline will be randomly assigned to usual care or to receive ACP informational website and video sent electronically to patients / proxies .

The primary clinical outcome will be the proportion of residents with DNR orders in the EHR at the end of four months followup. Secondary clinical outcomes will be: proportion of residents with do-not-hospitalize (DNH) orders in the EHR at the end of four months followup; proportion of residents with Medicare CPT billing code for ACP during the four months followup; and proportion of enrolled residents with any hospitalizations over four months (outcome available for FL ALCs only). Implementation outcomes include counts of emails and video views.

9.2 Sample Size and Randomization

Table 2 presents the number of ALCs per study arm required to detect varying levels of prevalence of DNR orders in the treatment arm for the 100 ALCs already randomized to the Information Only or Control study arms, assuming $\alpha=.05$, $\beta=.20$, and several values of the intra-class correlation coefficient (ICC). Based on baseline Bluestone data, we expect 54% of residents in the control arm will have a DNR order at the end of 4-months followup. Based on the same data, we estimated an ICC of 0.012 from the random intercept logistic model.⁴ Assuming a conservative ICC of .02, to achieve a power of .80, we need 71 ALCs per arm with 10 PLWD in each to demonstrate an 8-percentage point increase in DNR orders, such that information outreach would result in 62% of these residents having a DNR order at the end of 4-month follow-up.

Table 1. Number of ALCs required per study arm at varying effect sizes and values of the intra-class correlation coefficient (10 residents per cluster, **54% DNR among controls**)

Effect in Treated	Intraclass Correlation Coefficient (ICC)				
	0.010	0.015	0.020	0.025	0.030
0.60	117	121	126	131	136
0.61	85	89	92	96	99
0.62	65	68	71	73	76
0.63	51	53	56	58	60
0.64	41	43	45	47	48

In the additional 60 facilities, we expect only 26% of the residents in the control arm will have DNR order at the end of 4-months follow-up based on baseline Bluestone data (similar ICC to previously randomized facilities). Assuming a conservative ICC of .02, to achieve a power of .80, we need 79 ALCs per arm with 10 PLWD in each to demonstrate a 7-percentage point increase in DNR orders, such that information outreach would result in 33% of these residents having a DNR order at the end of 4-month follow-up (Table 3).

Table 3. Number of ALCs required per study arm at varying effect sizes and values of the intra-class correlation coefficient (10 residents per cluster, **26% DNR among controls**)

Effect in Treated	Intraclass Correlation Coefficient (ICC)				
	0.010	0.015	0.020	0.025	0.030
0.32	98	102	106	110	114
0.33	73	76	79	82	85
0.34	56	59	61	63	65
0.35	45	47	49	50	52
0.36	37	38	40	41	43

We will add 30 ALCs to the existing 50 ALCs per arm, resulting in 80 ALCs per arm. We will be able to detect between a 7- and 8-percentage point change in documentation of DNR orders in the EMR.

9.2.1 Treatment Assignment Procedures

Stratifying by state and balancing on baseline use of advance directives, number of Bluestone residents in the ALC, and resident clinical characteristics, a Brown statistician will randomize 160 ALCs to the intervention or control study arms (80 ALCs per arm).

9.3 Interim analyses and Stopping Rules

There will be no interim analysis and we do not include stopping rules for two reasons. First, this is a minimal risk study for which AEs will be rare. Second, a stopping rule would not be very feasible since the implementation period is less than one year— which means that interim data analyses will be difficult, if not impossible, to perform until the intervention is nearly complete.

9.4 Outcomes

9.4.1 Primary outcome

The primary clinical outcome will be the proportion of residents with DNR orders in the EHR at the end of four months followup.

9.4.2 Secondary outcomes

Secondary clinical outcomes will be: proportion of residents with do-not-hospitalize (DNH) orders in the EHR at the end of four months followup; proportion of residents with Medicare CPT billing code for ACP during the four months followup; and proportion of enrolled residents with any hospitalizations over four months (outcome available for FL ALCs only).

Implementation outcomes include counts of emails sent to patients/proxies and counts of website and video views.

9.5 Data Analyses

Our primary approach will be an intention-to-treat (ITT) analysis. Last observed advance directive status will be used for residents who are censored due to death or discharge after 2 months followup. Model specifications are based on Donner & Klar for cluster randomized controlled trials where Y_{ij} is the advance directive status for resident i from ALC j , and $\text{logit}(P(Y_{ij} = 1)) = \mu_{ij}$, where $\mu_{ij} = \mu + \alpha I_{ij} + \sum_{l=1}^L \gamma_{ijl} X_{ijl} + u_j$. We define $u_j \sim N(0, \sigma_u^2)$ as the conditional effect of ALC j on the logit scale, X_{ijl} are individual-level covariates, γ_{ijl} are unknown parameters, I_{ij} is an indicator for intervention arm membership, and α is the conditional treatment effect.

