3 STUDY DESIGN

This is a one year, embedded, pragmatic cluster-randomized trial (ePCT). ALCs will be randomly assigned to Usual care or ACP informational website and video sent electronically to family members. Stratifying by state and balancing on baseline use of DNR orders, number of Bluestone residents in the ALC, and resident clinical characteristics, a Brown statistician will randomize 160 ALCs to the intervention or control study arms (80 ALCs per arm).

Information materials include an email (Appendix A) with a link to a video describing resident goals of care and instructions for documenting treatment preferences in the form of advance directives or medical orders (Appendix B). When patients or proxies are not using the online portal, a letter and brochure reflecting the same content as the video will be sent to their residences. The materials were developed by [name], [name] and colleagues at Indiana University. [name] has agreed to modify their materials for the purposes of the study. In addition, all Bluestone clinicians will receive training (Appendix C) and a tailored conversation guide to help structure conversations with patients or proxies, when appropriate (Appendix D).

Residents and family members of eligible residents in ALCs randomized to the usual care arm have ACP discussions with a clinician at admission, annually, and sometimes with a hospitalization or other change in condition. There is no standardized decision- or conversation-support tools used to have these discussions. Clinicians will engage PLWD in advance care planning discussions as they would in usual care.

The primary clinical outcome will be the proportion of residents with DNR orders in the EHR at the end of four months followup. Secondary clinical outcomes will be: proportion of residents with do-not-hospitalize (DNH) orders in the EHR at the end of four months followup; proportion of residents with Medicare CPT billing code for ACP during the four months followup; and proportion of enrolled residents with any hospitalizations over

four months (outcome available for FL ALCs only). Implementation outcomes include counts of physician calls with family members and counts of website and video views. We plan to enroll approximately 3,000 patients and/or their proxies.

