4 SELECTION AND ENROLLMENT OF PARTICIPANTS

4.1 Inclusion Criteria

The unit of random assignment will be the ALC and the unit of analysis the resident, clustered within the ALC. We will use Bluestone's EHR data to identify eligible ALCs. Eligible ALCs will have at least 10 patients with a dementia diagnosis (ICD-10) who are not on hospice and do not have orders for comfort care or DNH at baseline.

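### The primary model omits wave, although the two pooled sets of ALCs expect control DNR rates of 54% and 26%, so the standard error is too large and power is lost

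*Combined protocol and SAP*

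**What the plan says.** Section 9.5 writes out one primary model: a logistic regression with an arm indicator, a sum of covariate terms and one normal random intercept per ALC with a common variance. The covariates are described only as "X_{ijl} are individual-level covariates". None is named, and the section mentions no wave, state or ALC-level factor.

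Section 9.2 sizes two sets of ALCs separately. For the 100 already randomised, the expected control DNR rate is 54%. For the rest: "In the additional 60 facilities, we expect only 26% of the residents in the control arm will have DNR order". The two are then combined: "We will add 30 ALCs to the existing 50 ALCs per arm, resulting in 80 ALCs per arm". From this the plan concludes: "We will be able to detect between a 7- and 8-percentage point change in documentation of DNR orders in the EMR".

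Section 9.2.1 describes the randomisation: "Stratifying by state and balancing on baseline use of advance directives, number of Bluestone residents in the ALC, and resident clinical characteristics". No section says how the analysis reflects these factors.

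**The concern.** The two waves differ by 28 points in expected control rate. ALCs are allocated 1:1 within each wave, so this difference cancels in the arm comparison. A model without wave cannot know that. It treats the gap as random variation between ALCs and carries it into the standard error of the arm effect.

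The ICC of 0.02 in the sample-size tables describes ALCs within one wave. It does not describe 160 ALCs drawn from two waves with very different rates. Each table also assumes a single control rate throughout, so the plan gives no power for the 50+30 design it will run. The risk is that a real effect of the planned size is missed, or reported with needlessly wide limits. A false positive is not the risk.

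**Working it through.** **Inputs.** Section 9.2: α = 0.05 (taken as two-sided), power 0.80, ICC ρ = 0.02, m = 10 residents per ALC, 54% to 62% in wave 1, 26% to 33% in wave 2, and 50+30 ALCs per arm. Section 3: "We plan to enroll approximately 3,000 patients and/or their proxies", which gives 3,000/160 = 18.75 per ALC. Equal cluster sizes are assumed. Below, 8/7 means 8 points in wave 1 and 7 in wave 2; 7/7 means 7 points in both.

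**1. The plan's own figures.** ALCs per arm = (1.960 + 0.842)² × [p₀(1−p₀) + p₁(1−p₁)] / (p₁−p₀)² × [1 + (m−1)ρ] / m, rounded up.
- 54% to 62%: 7.849 × 0.4840 / 0.0064 × 0.118 = 70.04, so 71, as stated.
- 26% to 33%: 7.849 × 0.4135 / 0.0049 × 0.118 = 78.2, so 79, as stated.

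The same formula reproduces all 50 cells of the two tables. Each calculation is right for a trial in which every ALC belongs to one wave.

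**2. True standard error of the pooled contrast.** The wave weights are 50/80 = 0.625 and 30/80 = 0.375.
- Average binomial variance, control: 0.625 × 0.2484 + 0.375 × 0.1924 = 0.2274.
- Average binomial variance, treated: 0.625 × 0.2356 + 0.375 × 0.2211 = 0.2302.
- Variance of the contrast: (0.2274 + 0.2302) × 0.118 / 80 = 0.000675, so SE = 0.0260.

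**3. Standard error reported without wave.** The between-wave variance is added.
- Control: 0.625 × 0.375 × 0.28² = 0.01838.
- Treated: 0.625 × 0.375 × 0.29² = 0.01971.
- Added: (0.01838 + 0.01971) / 80 = 0.000476. Total 0.001151, so SE = 0.0339.
- Ratio: 0.0339 / 0.0260 = 1.31.

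The control-arm ICC across both waves is (0.01838 + 0.02 × 0.2274) / (0.435 × 0.565) = 0.093. In the treated arm it is 0.097.

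**4. Power for 8/7.** The average effect is 0.625 × 0.08 + 0.375 × 0.07 = 0.0763.
- With wave: Φ(0.0763/0.0260 − 1.96) = 83.5%. The difference detectable with 80% power is 7.3 points.
- Without wave: Φ[(0.0763 − 1.96 × 0.0339) / 0.0260] = 64.6%. The detectable difference is 8.8 points.
- Type I error without wave: 2 × [1 − Φ(1.96 × 1.31)] = about 1.0%.

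**5. Other settings, closed form, none of the gap absorbed**

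| Setting | SE ratio | Power without wave | Power with wave |
|---|---|---|---|
| m = 10, 8/7, ICC 0.02 | 1.31 | 64.6% | 83.5% |
| m = 10, 7/7, ICC 0.02 | 1.30 | 56.0% | 76.7% |
| m = 18.75, 8/7, ICC 0.02 | 1.47 | 80.9% | 96.3% |
| m = 18.75, 7/7, ICC 0.02 | 1.45 | 72.3% | 93.0% |
| m = 18.75, 8/7, ICC 0.012 | 1.51 | 84.1% | 97.7% |

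**6. If covariates absorb part of the gap.** The between-wave variance shrinks with the square of the share left. For 8/7 at m = 10, absorbing 25%, 50% or 75% gives power without wave of 73%, 79% or 82%; 80% is reached at about 55%. At m = 18.75, absorbing 25% or 50% gives 89% or 94%.

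**7. Simulation of the random-intercept logistic model.** Two versions were run by maximum likelihood without covariates: beta-binomial data (1,500 trials per setting) and normal ALC intercepts (2,000 trials).
- 8/7 at m = 10: power 63.4% and 64.8% without wave, 83.5% and 83.4% with it.
- 8/7 at m = 19: 82.1% and 80.8% without, 96.9% and 96.2% with.
- No effect at m = 10: rejection 1.1% and 1.3% without, 5.5% and 6.2% with (Monte Carlo SE about 0.5 points).
- In the normal-intercept runs at m = 10, 8/7, the estimated log odds ratio is 0.338 either way. Without wave the mean model SE is 0.150 against an empirical SD of 0.118; with wave it is 0.115.

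**The case against.** The strongest objection is that the gap may not belong to the ALCs. Section 4.1 admits patients "who are not on hospice and do not have orders for comfort care or DNH at baseline", which allows a baseline DNR order. Section 6.2.2 counts residents "who are full code or missing code status at baseline". The plan does not say which definition produced 54% and which 26%. Suppose about 38% of first-wave residents had a DNR order at baseline and the rest converted at 26%: then 0.378 + 0.622 × 0.26 = 0.54. Baseline code status, which Section 10.1 lists among the EHR data, would explain the whole gap. This stands as a possibility, and it is why the loss is given as a range. It does not settle the matter, because no covariate is named. If all residents are full code or missing at baseline, a DNR covariate cannot separate the waves.

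Second, 10 per ALC is the eligibility minimum. At about 3,000 residents the 80% target is met for 8/7 without wave. That is correct, but about 15 points of power are still given up. The 7/7 case is an added scenario; the plan pairs 8 points with 54% and 7 with 26%.

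Third, the resident subscript on the covariates need not exclude ALC attributes, since arm carries the same subscript. The individual-level label points the other way, although resident clinical characteristics would fit it.

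Fourth, a single pooled analysis is inferred from the 80-per-arm statement and the single model. It is the natural reading.

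**Conclusion.** The concern holds. As written, the primary model does not secure adjustment for wave, and the 7- to 8-point claim in Section 9.2 rests on two single-wave calculations. With none of the gap absorbed, the loss for 8/7 is about 19 points of power at 10 per ALC and about 15 points at the planned enrolment. At 10 per ALC, power falls below 80% unless covariates absorb about 55% of the gap. If baseline code status is adjusted for and explains the gap, the loss could be close to nil.

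These figures assume the full 28-point gap, equal cluster sizes, ICC 0.02 within wave and one pooled analysis. They concern wave only: the documents give no DNR rates by state or balancing factor. This is a loss of efficiency, not of validity; no bias or excess of false positives is claimed. It should be fixed, with medium confidence in the size.

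**What to change.** - **Section 9.5, model terms:** pre-specify a fixed effect for wave. Also include state, ALC baseline directive use and number of Bluestone residents, so that the analysis matches the randomisation. The computed gain is for wave alone.
- **Section 9.5, covariates:** name the individual-level covariates, and say whether baseline code status is one of them.
- **Section 9.2, power:** add the power of the pooled 50+30 design at 10 per ALC and ICC 0.02: about 83.5% for 8/7 and about 77% for 7/7, both conditional on wave being in the model.
- **Sections 4.1, 6.2.2 and 9.2:** state which eligibility definition produced 54% and which produced 26%.

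The cost is a sentence or two in each place and a few degrees of freedom out of 160 clusters. No new data are needed: wave is known for every ALC, and the other factors were already used for randomisation. The terms should be fixed before outcomes are unblinded.

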10 DATA COLLECTION AND QUALITY ASSURANCE

10.1 Data Collection Forms

We will be receiving data from three pieces of Bluestone's integrated health information system: the primary EHR; the specialized Bridge interface with families and the care team; and the individual level capture of hospitalizations (FL ALCs only). Brown has an existing partnership with Bluestone [U54AG063546], for which we developed a Data Use Agreement. As we have done in previous trials, Bluestone IT staff will place a new copy of the data package in a SharePoint location each month. Brown IT staff will download the data into our secure environment, apply study identifiers, and create analytic data sets.

Specific data elements available from the EHR include:

- Resident and ALC identifiers
- Active diagnosis codes (ICD-10)
- Functional and cognitive status assessments
- Physician orders (treatments, diagnostic tests, etc.)
- Medication orders
- Advance directives / code status (full code, DNR, DNH, DNI, preference for comfort care)
- COVID testing results
- Hospitalizations (emergency department, ED, and observation stays, inpatient)

